On the day of the procedure, the research nurse will obtain the saline or Botox from the research pharmacy in a brown paper bag. She will then prepare the Botox or draw the normal saline and give it to the investigator for administration. In order to protect blinding, placebo and Botox will have the same characteristics, except for the active drug. The nurse who prepares the drug will also record the study arm in a file kept separate from patient information. Once this is recorded, information will be resealed and kept with patient information until the completion of the study. The nurse who prepared the composition will be the only unblinded member of the healthcare team and will not assist in the procedure.

The adverse effects will be assessed by one standard questionnaire, which allows the description of idiosyncratic reactions and 2 validated questionnaires, which assess the Botox specific adverse effects of fecal incontinence. Outcome measurements and assessment of adverse effects in the office will be made by a research nurse blinded to treatment group allocation.

The PI who delivers the intervention will not take outcome measurements and will have no interaction with the data collectors. The data collectors will be blinded throughout the data entry and data cleaning processes. The statistical analysis will be made after the end of the data collection period. The statistician will only be unblinded once the database is locked. At the end of the study, blinding integrity will be evaluated in a sample of participants and data collectors.

In case of medical emergency, if a study participant has encountered an urgent medical problem and the clinician needs to know his/her intervention group, the allocation code can be broken. Unblinding envelopes (labeled with the randomization number that contains allocation) are sealed by the study center and are only opened if emergency unblinding is necessary.

V. STUDY PROCEDURES

a. Study visits and parameters to be measured

As part of this research study, patients will be asked to come for three visits (Visit 1= return of informed consent and schedule of intervention; Visit 2= intervention; Visit 3=one month after the intervention). They will afterwards be contacted by mail with questionnaires and then with follow-up phone calls (for those who did not return questionnaires) to increase response rate at 3, 6 and 12 months after the intervention.

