All patients considered for the study will undergo pretreatment evaluation as per standard of care. This includes a history, clinical examination, and anorectal manometry. Once the patient is deemed eligible to participate, s/he will be offered the opportunity to participate in this trial.

If interested, s/he will meet with the Principal Investigator and/or research nurse practitioner to find out more about this trial. At this time all questions will be answered. Afterwards, s/he will be offered an informed consent form, for review at home. Patients will then be scheduled for a follow-up visit to review and sign consent with PI or study nurse practitioner.

Once all questions are answered and consent is signed, patients will be asked to fill out baseline questionnaires at the visit when consent is signed.

All questionnaires used in this study include validated scores. They will be used to assess the efficacy of the intervention in providing symptomatic improvement and improved quality of life (Altomare ODS score, generic SF-36 version 1, Patient Assessment of Constipation- Quality of Life questionnaire). We will also use 2 standard questionnaires to assess for Botox-specific adverse effects (Cleveland Clinic Fecal Incontinence Score and Fecal Incontinence Quality of Life Scale).

Patients will receive the questionnaires at baseline and then be asked to complete them at their one month follow-up visit.

At one month follow-up visit, patients will meet with their surgeon and the study nurse practitioner. They will first review any adverse reactions which they may have had. Patient will also be asked

about any adverse reactions which will be documented at that visit. They will then undergo anorectal manometry and fill out the questionnaires.

At 3, 6, and 12 months after the injection, patients will be mailed questionnaires. Those participants who do not respond within a month will be contacted by phone to increase response rate.

b. Drugs, devices and surgical procedures to be used

Patients are divided in 2 groups: Group #1: Placebo

Placebo consists of normal saline and has the same method and route of administration as the active treatment.

Group #2: Botox 100 IU

Each patient in Group #2 will receive a total of 100 units of botulinum toxin, stored in the research phramacy and dispensed to the clinic on the day of the procedure. Botox will be resuspended in 5 ml of sterile saline to a final concentration of 20 U/ml.

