For both groups, the interventions will be administered in the office under local anesthesia with 0.25% Marcaine stored in the clinic at 20° to 25°C. We plan to use a 10 mL single dose vial of Marcaine (Bupivacaine Hydrochloride Injection, USP 0.25% (2.5 mg/mL)) administered as local infiltration. More or less drug may be used depending on each individual case. The MGH **Research** Pharmacy will perform the computerized randomization and send up medication or saline in paper bag based on randomization of the subject. Both saline and Botox will be brought from research pharmacy on the day of the procedure in a brown paper bag.

The PI will use transanal ultrasound to clearly identify the puborectalis muscle. Once the muscle is identified, a 23-G needle will be used to inject the agent transanally into the puborectalis and external anal sphincter in three separate locations.

c. Data to be collected

All data are collected prospectively, at the pre-specified time points according to the protocol. All data will be collected in questionnaires attached (see above for specific description). Data from baseline manometry will be taken from patient chart and recorded into REDCap database where data will be stored. Anorectal manometry from 1-month follow-up will also be stored in REDCap database.

VI. BIOSTATISTICAL ANALYSIS

a. Specific data variables being collected for the study

Data collection sheets are attached to this submission. They include the MRN to facilitate data extraction, demographic information (age, sex, race), diagnostic tests at baseline and the study endpoints collected at pre-specified times.

b. Study Endpoints

a) Primary endpoint:

Baseline to 1 month after treatment changes in the sum of Altomare ODS score (ODS-S) and Patient Assessment of Constipation- Quality of Life score (PAC-QoL)

b) Secondary endpoints:

- Baseline to 1, 3, 6 and 12 months after treatment changes in Altomare ODS score (ODS-S) and Patient Assessment of Constipation- Quality of Life score (PAC-QoL)
- Changes in the generic SF-36 version 1, Cleveland Clinic Fecal Incontinence Score (CCFI) and Fecal Incontinence Quality of Life Scale (FIQoL) at 1, 3, 6 and 12 months from baseline
- Relaxation of puborectalis with push measured by EMG at 1 month
- Balloon expulsion test at 1 month
- Manometric changes at 1 month- changes in anal sphincter function (resting sphincter pressure, maximal resting anal pressure, maximum squeeze pressure).

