- Change in defecation index [Time Frame: Baseline, 1 month follow-up visit]. The defecation index=maximum rectal pressure during attempted defecation/minimum anal residual pressure during attempted defecation. This is calculated based on measurements obtained from anorectal manometry and is a measure of treatment efficacy.

c. Statistical methods

All analysis will be based on intention-to-treat population in that all randomized subjects will be included in the analysis.

Data will be expressed as mean+/- standard deviation (SD) for all continuous outcomes, and as counts and proportions for all categorical outcomes. The primary analysis (i.e., the comparison of 1-month change in mean ODS-S and PAC-QoL between the 2 treatment arms) will be made by independent samples t-test. Comparison of treatment effect over time (i.e., 1- and 3-, 6- and 12 months) on all scale scores will be performed by using longitudinal linear mixed effects model, which allows to specify the subject specific baseline levels and the time dependent response trajectories (i.e., slopes) random (SAS proc mixed). All p-values are two-tailed and considered significant if p<0.05.

d. Power analysis

The proposed sample size is 46 (i.e., 23 in each treatment arm). With an assumption of an attrition rate of up to 15%, we anticipate to attain 40 study completers. The study is designed to detect at

least 25% decrease in mean ODS-S and PAC-QoL at 1 month after treatment with Botox with 80% power at a 5% significance level. This effect size of \geq 25% is equivalent to a decrease in mean ODS-S decrease from 15 points at baseline to \leq 11.4 points at 1 month³⁷⁻³⁸. **VII. RISKS AND DISCOMFORTS**

a. Complications of surgical and non-surgical procedures

We do not expect any unusual safety concerns in this study. The small foreseeable discomforts and complications will be treated as per standard of care.

b. Drug side effects and toxicities

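### The primary change-score t-test cannot include a patient without a 1-month score, although the plan promises to analyse everyone randomised, and it leaves the collected baseline score unadjusted

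*Combined protocol and SAP*

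**What the plan says.** Section VI.c defines the analysis population as intention-to-treat, in that "all randomized subjects will be included in the analysis". For the primary analysis it states that "the comparison of 1-month change in mean ODS-S and PAC-QoL between the 2 treatment arms) will be made by independent samples t-test". Section VI.b defines the primary endpoint as the baseline-to-1-month change in the sum of the two scores.

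Section VI.d anticipates losses: "With an assumption of an attrition rate of up to 15%, we anticipate to attain 40 study completers". The figure is not tied to a visit.

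Three other provisions bear on the point:

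- **Collection (V.a).** Baseline questionnaires are filled in at the consent visit. For month 1, "Patients will receive the questionnaires at baseline and then be asked to complete them at their one month follow-up visit". Recovery is described only for the mailed rounds, by "follow-up phone calls (for those who did not return questionnaires) to increase response rate at 3, 6 and 12 months after the intervention".
- **Mixed model (VI.c).** A linear mixed model with random subject levels and slopes is planned for "Comparison of treatment effect over time (i.e., 1- and 3-, 6- and 12 months) on all scale scores". It covers month 1 but is not the primary test.
- **Blinding (IV.c).** "The statistician will only be unblinded once the database is locked".

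The documents state no imputation method, no missing-data assumption and no sensitivity analysis for a missing 1-month score.

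**The concern.** A change score needs both ends. If the 1-month value is absent, the t-test must omit the patient or use an assigned value, and the plan does not say which. Omitting, carrying forward and imputing can give different primary results from the same data. Omission, the literal reading, also breaks the promise to include everyone randomised.

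The second matter is efficiency. A change-score t-test fixes the coefficient of baseline at 1. In a randomised comparison that causes no bias, but estimating the coefficient is at least as efficient apart from one degree of freedom, and the baseline score is already collected.

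**Working it through.** **1. Losses, from VI.d.** 46 - 40 = 6 patients, and 6/46 = 13.0%. At the 15% ceiling, 46 x 0.15 = 6.9. The stated 40 completers therefore agree roughly with 46 x 0.85 = 39.1.

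**2. The effect behind the 80% power.** This cannot be reproduced directly because no SD is stated. Solving instead: a two-sample t-test with 20 per arm, two-sided 5%, 38 df (critical t 2.024) has 80% power at d = 0.909 SD of change. The standard error is sqrt(2/20) = 0.316 SD. With the ODS-S fall from 15 to 11.4 points in VI.d, the implied SD of change is 3.6/0.909 = 3.96 points.

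**3. Bias from omitting lost patients.** Let m be the number lost in an arm of 23, and g the mean improvement of those seen minus that of those lost. The observed arm mean exceeds the full arm mean by m x g/23, so

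bias in the arm difference = (m_Botox x g_Botox - m_placebo x g_placebo)/23.

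- Three lost per arm, equal gaps: bias 0.
- Three lost per arm, gap in one arm only (g assumed): 3 x 0.5/23 = 0.065 SD, or 3 x 1/23 = 0.130 SD, in either direction. These are 7.2% and 14.3% of 0.909.
- One such loss in one arm: 0.5/23 = 0.022 SD, or 1/23 = 0.043 SD.

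For the cases of 0.065 and 0.130 SD, the noncentral t distribution (38 df, noncentrality = shift/0.316) gives:

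- bias favouring Botox, no true effect: chance of a false positive for Botox 3.9% and 6.0%, against 2.5%;
- bias against Botox, true effect 0.909 SD: power 73.9% and 67.0%, against 80%.

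**4. Baseline adjustment in the same 40 patients.** Let r be the correlation of baseline with the 1-month score, and k the baseline SD divided by the 1-month SD. The documents give neither.

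Variance ratio, ANCOVA to change score = (1 - r^2)/(1 + k^2 - 2rk).

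The cost of the covariate is allowed for by 37 df and a factor of 37/36. Example, k = 1 and r = 0.5: 0.75/1 = 0.75, giving 89.0% power.

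| Power of ANCOVA (t-test = 80%) | r = 0.3 | r = 0.5 | r = 0.7 |
|---|---|---|---|
| k = 1 | 92.9% | 89.0% | 85.0% |
| k = 0.7 | 85.0% | 80.9% | 78.9% |
| k = 0.5 | 80.6% | 78.9% | 81.8% |

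The range is -1.1 to +12.9 points overall, and -1.1 to +5.0 for k of 0.5 to 0.7. A k below 1 is plausible because III.a requires an ODS-S of at least 15 at entry, but only that part of the sum has a cut-off.

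**5. What imputation adds.** In simulations with 23 per arm and three lost at random in each (k = 1, 20 imputations from arm and baseline), power for r = 0.3, 0.5, 0.7 was 93.2%, 89.0%, 85.2% for observed-case ANCOVA and 92.6%, 88.4%, 84.2% for imputed ANCOVA. Imputation brings in all 46 but adds no power.

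With Botox losses weighted towards poor change (r = 0.5, no true effect), bias was 0.48 points for the t-test and 0.36 for imputed ANCOVA, so 0.36/0.48 = 75% of it remained. Type I error was 7.3% and 6.1%.

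**The case against.** The strongest reply is that the t-test is a valid, pre-specified test and the losses may be small. Much of this stands.

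- **Validity.** A reader might infer that the change-score t-test is itself biased. It is not: with complete data, randomisation makes it unbiased. Preferring ANCOVA is a matter of efficiency.
- **Losses at month 1.** A reader might infer that six or seven primary scores will be missing. The 15% refers to completers of a study that runs to 12 months. Month 1 is an in-person visit, and IX.c has the principal investigator monitor data completeness. Step 3 uses the full six losses and an assumed gap in one arm, so it shows an adverse case.
- **Direction.** A reader might infer a bias towards Botox. VII.b mentions discomfort if incontinence occurs, and VII.d mentions frustration in the control group. Neither is linked to dropout, so bias may be zero or go either way.
- **ANCOVA and intention-to-treat.** A reader might infer that ANCOVA delivers the promise to include everyone. It drops the same patients as the t-test. Only imputation or a likelihood model brings them in.
- **Size of the gain.** The +13 points occurs only at k = 1 and r = 0.3, the most favourable case assumed.

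Blinding of the statistician until database lock limits biased choices, but it does not say which rule applies. The planned mixed model could use partial data, but VI.c does not make it primary. Even one missing 1-month score would leave the primary result undetermined by the text.

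**Conclusion.** The point holds. Read literally, VI.c makes the primary result an observed-case analysis under an intention-to-treat label, with up to 6 or 7 of 46 lost over the study and possibly fewer by month 1. The bias is unknown in size and sign: zero under equal loss and equal gaps, and 0.07 to 0.13 SD in the adverse case assumed. Separately, ANCOVA on the existing baseline score is a better primary test in most of the settings examined and costs about 1 point of power in the least favourable. The power figures rest on assumed correlations and SD ratios and on an effect back-solved from the stated power. The plan remains workable, so this is a change that should be made rather than a fatal flaw. Confidence is medium.

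**What to change.** 1. **Primary test.** Use ANCOVA of the 1-month primary score on arm and baseline score.
2. **Include all 46.** Choose one of two routes in advance; either is acceptable.
   - Multiple imputation of missing 1-month scores from arm, baseline and the 3, 6 and 12-month scores (for example 50 sets), with Barnard-Rubin degrees of freedom and a stated missing-at-random assumption.
   - In place of the ANCOVA, the 1-month contrast of the mixed model already planned, with visit as a category and baseline as a response. Name the covariance structure, a fallback and Kenward-Roger degrees of freedom.
3. **Sensitivity.** Keep the observed-case t-test. Add one shift analysis that worsens imputed 1-month scores by 0, 0.5 and 1 SD in Botox only, placebo only and both, and reports where the conclusion changes. Say which SD is used. This is needed because imputation only partly reduces bias from informative loss.
4. **Partial forms.** State the rule when only one component of the sum, or some of its items, is missing.
5. **Collection.** Extend the mail and phone follow-up to missed 1-month questionnaires.

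**Cost.** One SAP paragraph, modest code and up to 6 or 7 extra contacts, with no new measures. ANCOVA costs one degree of freedom. In a further simulation of imputed ANCOVA with random loss (20 imputations), the worst case lost 3 points of power against the t-test (78.4% to 75.4%, at k = 0.5 and r = 0.5, imputing from arm and baseline only). The mixed model with five visits and a common baseline needs 1 + 4 x 2 = 9 mean parameters and up to 5 x 6/2 = 15 covariance parameters. A joint imputation model for the same scores is of comparable size, so neither route is shown to be cheaper.

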Patients treated with Botox will have an improvement in the Altomare Obstructed Defecation Syndrome score (ODS-S) and Patient Assessment of Constipation- Quality of Life Score (PAC-QoL) compared to the placebo group.

III.SUBJECT SELECTION

a. Inclusion/exclusion criteria

Inclusion criteria

- Males and females older than 18 years of all races and backgrounds
- Competent to give informed consent
- Meet the Rome III diagnostic criteria for functional constipation
- Inability to relax the puborectalis muscle at electromyography
- Altomare Obstructed Defecation Syndrome score of 15 points or above
- Failure of treatment with 2 conservative measures which may be as follows:
 - 1 laxative (osmotic or stimulant) for 2 weeks
 - 1 fiber supplement for one month
 - o And/or trial of biofeedback for at least 4 sessions

Exclusion criteria

- Previous treatment with botulinum toxin (possible antibodies)
- Known hypersensitivity to any of the components of the toxin
- Presence of allergy or allergic reaction to bupivacaine
- Medication regimen includes narcotics
- Previous radiation therapy to the anal canal and rectum
- Prior proctectomy
- Presence of unhealed and symptomatic anal fissure
- Presence of anal pain
- Presence of fecal incontinence
- Presence of full thickness rectal prolapse
- Presence of internal sphincter myopathy
- Inflammatory bowel disease or proctitis
- Pregnancy or breast-feeding
- Subject is currently enrolled/ just finished participating in a clinical trial in which the intervention/ its carry-over effect may interact with the intervention in this trial

b. Source of subjects and recruitment methods

All patients seen through the Pelvic Floor Disorder Service in colorectal surgery and gastroenterology at MGH who are diagnosed with outlet obstruction will be told about the option to participate in the study by their treating physician/ nurse practitioner.

IV. SUBJECT ENROLLMENT

a. Methods of enrollment

We will enroll 23 patients into the control and 23 patients into the placebo arm of the study. All patients with ODS who are evaluated in the Pelvic Floor Disorders Service at MGH through colorectal surgery and gastroenterology will be informed of the study.

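### The primary t-test on raw 1-month change leaves the collected baseline scores out as a covariate; pre-specifying ANCOVA is a nearly free gain in precision, of uncertain size

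*Combined protocol and SAP*

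**What the plan says.** VI.b (Study Endpoints) defines the primary endpoint as "Baseline to 1 month after treatment changes in the sum of Altomare ODS score (ODS-S) and Patient Assessment of Constipation- Quality of Life score (PAC-QoL"). VI.c (Statistical methods) gives the primary analysis as "the comparison of 1-month change in mean ODS-S and PAC-QoL between the 2 treatment arms) will be made by independent samples t-test". No covariate is named and no reason is given for leaving baseline out. A linear mixed model with subject-specific baseline levels is also planned in VI.c, but for the treatment effect over 1, 3, 6 and 12 months, not for the primary test.

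The baseline values will exist. V.a states that "patients will be asked to fill out baseline questionnaires at the visit when consent is signed", which is before the intervention visit. IV.c describes 1:1 allocation in permuted blocks of varying size and names no stratification factor. III.a requires an "Altomare Obstructed Defecation Syndrome score of 15 points or above".

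VI.d (Power analysis) states "The proposed sample size is 46 (i.e., 23 in each treatment arm") and "With an assumption of an attrition rate of up to 15%, we anticipate to attain 40 study completers". It claims to detect a 25% decrease "with 80% power at a 5% significance level". VI.c makes all tests two-sided at 0.05. VI.d gives no SD, no correlation between baseline and 1 month, and no expected change on placebo.

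**The concern.** A change score uses baseline in one fixed way: it subtracts the whole of it, which amounts to assuming that the 1-month score rises one point for each baseline point. ANCOVA estimates that slope from the data. Patients are enrolled because their ODS-S is high, so some regression to the mean is expected and a slope below 1 is plausible. If so, subtraction over-corrects and leaves avoidable variance in the treatment contrast.

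With about 20 completers per arm and no stratification on severity, neither design nor analysis removes that variance. What is at stake is the width of the confidence interval and the chance of missing a real effect in a small trial. The point is separate from how missing 1-month scores are handled.

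**Working it through.** **Inputs from the documents:** 46 randomised, 40 expected completers (20 per arm), two-sided 5%, 80% power (VI.c, VI.d). **Assumed, because the documents are silent:** the correlation ρ between baseline and 1-month score, and k = baseline SD / 1-month SD.

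**1. The plan's own figure.** The 80% cannot be reproduced without an SD. Solving the noncentral t for 20 per arm (38 df) shows what it implies: a between-arm difference of 0.909 SD of change. The fall from 15 to 11.4 in VI.d is 3.6 points, so the implied SD of change is 3.6 / 0.909 = 3.96 points if placebo does not change. At 23 per arm the implied difference is 0.845 SD.

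**2. Variance ratio.** With the 1-month variance set to 1, change has variance 1 + k² − 2ρk and the ANCOVA residual has variance 1 − ρ². The difference is (k − ρ)². It is never negative, and it is zero only when ρ = k, that is, when the slope ρ/k equals 1. With equal SDs the ratio of ANCOVA to change variance is (1 − ρ²) / (2(1 − ρ)) = (1 + ρ)/2.

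**3. Power.** The t-test is held at 80% with 20 per arm. Each ratio is multiplied by 1 + 1/36 for estimating the slope, and df is set to 37. Example, ρ = 0.5 and k = 1: 0.75 × 37/36 = 0.771; 0.909 / √0.771 = 1.035; noncentrality 1.035 × √10 = 3.27; power 89.0%. A simulation of 100,000 trials also gave 89.0%.

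| k | ρ | Slope ρ/k | Variance ratio | ANCOVA power |
|---|---|---|---|---|
| 1 | 0.3 | 0.3 | 0.65 | 92.9% |
| 1 | 0.5 | 0.5 | 0.75 | 89.0% |
| 1 | 0.7 | 0.7 | 0.85 | 85.0% |
| 1 | 0.8 | 0.8 | 0.90 | 82.9% |
| 0.75 | 0.3 | 0.40 | 0.818 | 86.3% |
| 0.75 | 0.5 | 0.67 | 0.923 | 82.0% |
| 0.75 | 0.7 | 0.93 | 0.995 | 79.1% |
| 0.5 | 0.3 | 0.60 | 0.958 | 80.6% |
| 0.5 | 0.5 | 1.00 | 1.000 | 78.9% |
| 0.5 | 0.7 | 1.40 | 0.927 | 81.8% |

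If the 80% is tied to 23 per arm instead, the equal-SD results barely move: 93.0%, 89.2% and 83.1% at ρ = 0.3, 0.5 and 0.8.

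**4. Explicit truncation of baseline.** Take ρ = 0.5 and equal SDs before selection (slope 0.5, residual variance 0.75). A cut 1 SD below the mean leaves baseline variance 0.630. Change variance is 0.75 + 0.25 × 0.630 = 0.907, the ratio is 0.75 / 0.907 = 0.826, and power is 85.9%. A cut at the mean leaves variance 0.363, ratio 0.75 / 0.841 = 0.892, and power 83.2%.

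**5. Chance imbalance.** The SD of the baseline mean difference is √(2/20) = 0.316 baseline SD, and its expected absolute size is 0.316 × √(2/π) = 0.252 SD. At slope 0.5, half of this (about 0.13 SD) enters the change-score contrast. It is already counted in the variance in step 2.

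**The case against.** The planned test is pre-specified, matches an endpoint defined as a change, and under 1:1 randomisation is unbiased with correct type I error. Baseline is used, though only by subtraction. All of this stands. A reader might infer that chance baseline imbalance biases the primary result; the documents do not support that. Imbalance averages to zero under randomisation and its contribution is inside the t-test's standard error, so it is the same precision loss seen from another side.

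A reader might also infer that the trial gives up nine points of power, 80% against 89%. That figure needs ρ = 0.5 and equal SDs, neither of which is in the documents. The entry cut that makes regression to the mean plausible may also narrow the baseline spread, which shrinks the gain, in some cases to nothing. VI.d even uses 15, the entry minimum, as the baseline mean of ODS-S. Against this, the cut applies to ODS-S only. PAC-QoL has no entry cut, so the spread of the sum may be narrowed less.

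Nor should the 80% be read as power with complete data. If it belongs to the 40 completers, the t-test with all 46 complete would have about 85%, and ANCOVA about 93% at ρ = 0.5 with equal SDs. The 80% is itself unverifiable, since VI.d describes a fall after Botox rather than a difference between arms.

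The mixed model does not answer the point, because VI.c does not assign it to the primary comparison.

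**Conclusion.** The point holds as one of efficiency, and the change is a free improvement rather than the repair of an error. The primary test leaves out a prognostic covariate that is already collected, and it loses precision unless the true baseline slope is 1. Taking the stated 80% as the power of the change-score t-test at 20 per arm, ANCOVA would give about 83% to 93% with equal SDs (ρ from 0.8 to 0.3). With a baseline SD of 0.5 to 0.75 of the 1-month SD (ρ from 0.3 to 0.7) it would give about 79% to 86%. The effect on power therefore runs from a loss of about 1 point to a gain of about 13. A material gain is plausible but not shown, because SD and correlation are assumed throughout.

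**What to change.** In VI.c, replace the independent-samples t-test as the primary analysis with a linear model (ANCOVA) of the 1-month score on treatment arm plus the baseline value of the same score. If the sum named in VI.b is the primary outcome, use the baseline sum as the covariate. Report the adjusted arm difference with its 95% CI and two-sided p-value, and keep the change-score t-test as a sensitivity analysis. In VI.d, state the assumed SD and baseline-to-1-month correlation, and give any expected power gain as a range.

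The cost is a sentence or two of text and one further model call. No new data, visits or patients are needed. The statistical price is one degree of freedom, about 1 power point at worst. The change should be made before unblinding, so that the choice of adjustment cannot appear to depend on the result.
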